#### *Delay Discounting Task*

Detailed methods have been previously described and validated in a similar subject population (Boettiger et al., 2007; Mitchell et al., 2005). At the start of each trial, subjects were cued to one of four trial types: “Want”, “Don’t Want”, “Sooner”, and “Larger”. For each of these trial types, subjects were presented with two hypothetical alternatives on the left and right sides of the screen: a smaller amount of money available sooner and a larger amount available at a future point in time. Subjects made a button press to select the option associated with the left and right sides of the screen in accordance with trial type. Subjects selected the option they wanted in the “Want” trials and the option they did not want in the “Don’t Want” trials. “Sooner” and “Larger” trials, in which subjects simply identified the sooner and larger options respectively, were included as control conditions to ensure that subjects followed task instructions. The choice was

presented as one of six variations: a “sooner” option of “today” versus a “later” option of five future time points (1 week, 2 weeks, 1 month, 3 months, or 6 months), or a “sooner” option of “3 months” versus a “later” option of “6 months”. The “larger” value consisted of six amounts (\$1, \$2, \$5, \$10, \$20, or \$100), while the “sooner” value represented one of four percentages (70%, 85%, 90%, and 95%) of the larger delayed amount. Subjects completed 6 blocks of 47 trials each (for a total of 282 trials) presented in pseudorandom order and were permitted to take breaks between each block. The “Want” condition comprised 50% of all trials, the “Don’t Want” condition comprised 34%, and the two control conditions combined comprised 16% of the trials. The primary behavioral outcome was the impulsive choice ratio (ICR), which represents the ratio of the number of sooner choices to the number of total choices in the “Want” condition. More impulsive subjects are thus characterized by higher ICR values. Previous work has demonstrated that this intuitive score correlates strongly with other model-based measures of delay discounting (Kayser et al., 2012; Kayser, Mitchell, Weinstein, & Frank, 2015; Mitchell et al., 2005). Study participants completed this task together in the same testing room prior to the laboratory bar.

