#### *Statistical Analysis*

Our sample size was calculated based on previous changes in alcohol consumption observed in a laboratory bar setting (Mitchell, Bergren, Chen, Rowbotham, & Fields, 2009). We calculated that, for a mean difference of .5 drinks per session and a standard deviation of 1.2 drinks, we would need a sample size of at least 48 subjects to achieve an alpha of .05 with a power of .80 for the pilot group laboratory bar protocol. Due to low enrollment and high drop-out rates in this subject population, we projected that we would need to enroll 80 subjects to achieve a final sample size of 48 subjects.

We enrolled a total of 62 enrolled subjects, and 55 subjects successfully completed the weekend drinking paradigm. Of the 7 subjects who did not complete the paradigm, 1 was excluded for non-adherence to the study protocol, 1 asked to withdraw, 1 experienced a drug dispensing error, 1 did not show for the scheduled visit, and 3 subjects had positive urine drug screens at the first lab bar visit and ended their participation. 50 of 55 subjects completed both lab bar sessions. The 5 who did not complete both lab bar sessions had positive urine drug screens and were excluded from drinking at these sessions. Three additional subjects were excluded from the DDT decision making task analysis for performing at less than 60% accuracy on control trials designed to assess task compliance (Mitchell et al., 2005), leaving 47 subjects for the DDT analysis.

The primary outcome measure of “weekend drinking” was defined as total number of alcoholic drinks consumed (Friday to Sunday) to capture drinking on study drug across dosing schedules. Secondary outcome measures included the change in impulsive choice ratio (ICR) on the DDT task following tolcapone, the number of alcoholic drinks consumed in the lab bar, and the impact of genotype on tolcapone effects. Data is reported as mean  $\pm$  SEM unless otherwise noted.

Change in weekend drinking and ICR on tolcapone versus placebo were assessed using a within subjects paired t-test. Differences in DDT responses across genotypes were assessed using a one-way ANOVA. The relationship between tolcapone effects on weekend drinking and ICR was assessed with correlation analysis. All statistical tests were conducted using VassarStats and Microsoft Excel V15.23.2.

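### Does the plan need to name a test and an analysis set for lab-bar drinks, the outcome that set its sample size?

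*Combined protocol and SAP*

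**What the plan says.** All of this is in the Statistical Analysis section unless another section is named.

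- **Sizing.** For a difference of 0.5 drinks per session and an SD of 1.2, the authors state that "we would need a sample size of at least 48 subjects to achieve an alpha of .05 with a power of .80". The calculation is for the laboratory bar.
- **Status of the outcome.** Weekend drinking is primary. Secondary outcomes include "the number of alcoholic drinks consumed in the lab bar".
- **Named tests.** There are three. The comparison of drug with placebo is covered by this sentence: "Change in weekend drinking and ICR on tolcapone versus placebo were assessed using a within subjects paired t-test". The genotype analysis has its own method: "Differences in DDT responses across genotypes were assessed using a one-way ANOVA". The link between the two drug effects is the third: "The relationship between tolcapone effects on weekend drinking and ICR was assessed with correlation analysis". None covers lab-bar drinks.
- **Analysis sets.** For delay discounting the number is explicit: "leaving 47 subjects for the DDT analysis". For the bar there is a completion count, "50 of 55 subjects completed both lab bar sessions", with the reason the other five are missing: positive drug screens, so they were not allowed to drink.
- **Grouping.** Screening Visit and Laboratory Session describe groups of 4 to 8. Under Delay Discounting Task, "Study participants completed this task together in the same testing room prior to the laboratory bar". Experimental Design and Crossover both speak of subjects crossing over to the other drug. The visible text does not state the unit to which drug order was assigned.

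**The concern.** The outcome that justifies the sample size is the one comparison of drug with placebo that has no named test. The 0.80 power belongs to a particular analysis, and a reader cannot confirm from the text that this analysis produced the lab-bar result. An unnamed test also leaves room to choose among several once the data are in.

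The second worry is clustering. Subjects drank together and were encouraged to interact. If every member of a group had the same drug order, a good or bad evening for the group would be mixed up with the drug effect. An ordinary paired t-test would then reject too often, and 48 subjects would carry less information than the calculation assumes. Because the delay discounting task was also done in a shared room, the same question could reach the impulsive choice ratio.

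**Working it through.** **1. Reproduce the planned figure.** Inputs from Statistical Analysis: difference 0.5, SD 1.2, alpha 0.05, power 0.80, n = 48. Two assumptions are needed because the text is silent: 1.2 is the SD of within-subject differences, and alpha is two-sided.

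- Standardised difference: 0.5 / 1.2 = 0.4167.
- Normal approximation: n = [1.2 × (1.960 + 0.842) / 0.5]² = 45.2, so 46.
- Exact paired t-test: noncentrality 0.4167 × √48 = 2.887 on 47 df gives power 0.807. At n = 47 power is 0.799, so 48 is the smallest adequate size.
- Alternatives that do not reproduce 48: a one-sided paired t-test needs 38, and a two-sample t-test needs 91 per arm.

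The sizing therefore identifies a two-sided paired t-test, the method the section names for the other two comparisons of drug with placebo.

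**2. Power in the implied set.** With 50 completers, noncentrality is 0.4167 × √50 = 2.946 on 49 df, and power is 0.823. The target of 48 was met.

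**3. How much the choice of subject-level test matters.** A period-adjusted comparison of session differences between the two orders (46 df) has power 0.807, the same as the paired t-test at n = 48. A simulation used whole drinks capped at 0 to 4, as in the bar. It assumed a latent placebo mean of 2 or 3, was tuned to a mean difference of 0.50 and SD of 1.20, and had n = 48 and 20,000 runs:

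| Test | Power (mean 2 / mean 3) |
|---|---|
| Paired t | 0.798 / 0.806 |
| Signed-rank | 0.793 / 0.799 |
| Period-adjusted | 0.798 / 0.806 |

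Under no drug effect each test rejects in 0.045 to 0.050 of trials. Reporting whichever of the three is most favourable rejects in 0.053 to 0.054.

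**4. When the unit of assignment would matter.** The documents give no intracluster correlation (ICC), so 0.05 to 0.20 is an assumed range. If whole groups of size m share an order, the variance of the mean difference is multiplied by 1 + (m − 1) × ICC, and the paired t-test has type I error of roughly 2 × [1 − Φ(1.96 / √design effect)].

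- m = 4, ICC 0.05: design effect 1 + 3 × 0.05 = 1.15, type I error 0.068.
- m = 8, ICC 0.20: design effect 1 + 7 × 0.20 = 2.40, type I error 0.206.

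Simulation with 48 subjects (20,000 runs) gave 0.069 and 0.210 for these two cases. With order assigned individually within groups, over the same ICC range, it gave 0.047 to 0.051. So the paired t-test is sound under individual assignment even when group members share an evening effect.

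**The case for a change.** The best case for a change is that the fix is cheap and the omission sits on the outcome behind the sample size. One sentence would name the test and the 50 completers, and another would give the unit of assignment. It is also fair that the text does not say whether a session in which a subject was barred from drinking counts as missing or as zero drinks. Further, if whole groups shared an order, a valid group-level test would have lower power: 0.740, 0.674 or 0.588 for groups of 4, 6 or 8 at an ICC of zero, against 0.807.

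The omission stands as a matter of reporting. The rest carries less weight.

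- A barred session yields no choice about drinking, so treating it as missing is the natural reading. The text already counts those five as not having completed both sessions.
- The lower group-level powers are the price of guarding against correlation. They do not show that 0.80 is wrong, and they apply only if whole groups shared an order. The harm in that case would be the inflated type I error in step 4 of the working.
- No visible passage says that groups shared an order. Subjects are described as the units that crossed over, and the groups of 4 to 8 are described as scheduling. The design figure is not shown in the copy reviewed, so the unit cannot be called missing from the plan.
- The document is written after the fact, with compliance results and final counts. A sentence added now would disclose the test but could not show that it was fixed in advance.

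One limit remains under individual assignment: people drinking together may influence each other, so one member's drug effect could alter another's count. Naming the test would not remove that.

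**Conclusion.** No change to the plan is needed. This is a gap that analysts fill sensibly: a paired t-test on the 50 two-session completers follows from the sizing, from the method used for the sister outcomes and from the counts given. The size of the demonstrated gap is negligible, with subject-level power of 0.79 to 0.81 whichever test is used at n = 48 and a type I error of about 0.053 under the most favourable choice of three. The outcome is secondary and described as proof of principle, and the test for the primary outcome is named.

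The conclusion assumes that 1.2 is the SD of differences, that alpha is two-sided, and that drug order was assigned by subject. If whole groups shared an order and outcomes were correlated within groups, the paired t-test would be anticonservative, at about 0.07 to 0.21 over the assumed ICC range. The visible text neither states nor suggests that arrangement.

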#### *Genetic Analysis*

Although our sample size was not powered to examine genotype, an exploratory analysis was conducted to ascertain whether the previously published relationship between COMT and decision-making might also be apparent in this study sample. DNA was extracted from saliva samples by the UCSF Genomics Core using Gentra Puregene reagents and protocols and quantified using the Pico Green method (Molecular Probes/Invitrogen). COMT genotyping was carried out by direct DNA sequencing of genomic DNA using fluorescent Sanger chemistry and analyzed using Mutation Surveyor from SoftGenetics LLC. Sequencing genotype accuracy was cross-validated with TaqMan (Applied Biosystems, Foster City, CA).

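### Does the one-way ANOVA of DDT responses fail to test the listed genotype outcome?

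*Combined protocol and SAP*

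**What the plan says.** Three places bear on the point.

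- **Statistical Analysis, outcome list.** The secondary outcomes include "the change in impulsive choice ratio (ICR) on the DDT task following tolcapone", lab-bar drinks, "and the impact of genotype on tolcapone effects".
- **Statistical Analysis, methods.** Three consecutive sentences give the tests. First: "Change in weekend drinking and ICR on tolcapone versus placebo were assessed using a within subjects paired t-test". Then the only genotype method in the document: "Differences in DDT responses across genotypes were assessed using a one-way ANOVA". Then: "The relationship between tolcapone effects on weekend drinking and ICR was assessed with correlation analysis".
- **Genetic Analysis.** "Although our sample size was not powered to examine genotype, an exploratory analysis was conducted"; its purpose was to see "whether the previously published relationship between COMT and decision-making might also be apparent in this study sample".

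The Delay Discounting Task section defines the measure itself: "The primary behavioral outcome was the impulsive choice ratio (ICR), which represents the ratio of the number of sooner choices" to total choices in the Want condition. That is a value for one session. The DDT analysis has 47 subjects and weekend drinking has 55.

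**The concern.** The listed outcome is a genotype-by-drug question. In a two-period crossover it is answered by comparing each subject's tolcapone-minus-placebo difference across genotypes. The ANOVA sentence mentions no difference, although the sentences before and after it both refer to the tolcapone effect. The stated genetic aim also has no drug term. A reader could conclude that the ANOVA was run on ICR itself, from one session or averaged over two.

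That would matter for the genotype claim. An ANOVA on ICR level responds to any association between COMT and impulsive choice, whether or not tolcapone does anything. A significant result could then be reported as genotype modifying the drug effect when it shows only that genotypes differ in impulsivity.

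A second gap appears on either reading. The outcome list does not restrict tolcapone effects to ICR, yet no genotype test is given for weekend drinking (the primary outcome) or for lab-bar drinks.

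**Working it through.** **Step 1. The two readings.**

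| Evidence | Points to |
|---|---|
| ICR is defined per session (Delay Discounting Task) | level |
| Aim is COMT and decision-making, no drug term (Genetic Analysis) | level |
| ANOVA sentence names no drug contrast; its neighbours do | level |
| DDT secondary outcome is listed as the change in ICR (Statistical Analysis) | change |
| Listed genotype outcome concerns tolcapone effects (Statistical Analysis) | change |
| One-way ANOVA needs one value per subject | change, weakly; a single-session or averaged ICR also qualifies |

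The text does not settle the matter. On the change reading the stated test is already right.

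**Step 2. How far the readings differ.** The plan gives no genotype figure to reproduce. Assumptions, none of them in the documents: all 47 subjects genotyped, three groups coded 0, 1, 2 alleles, counts 12/23/12 or 6/22/19, additive effect, between-session correlation ρ of 0.5 or 0.8, alpha 0.05.

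Power is P(F′ > F₀.₉₅(2, 44)), where F′ is noncentral F with λ = b² × S. Here b is the effect per allele in SD units of the analysed variable and S is the sum of squared deviations of allele count.

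- 12/23/12: mean 1, S = 12 + 12 = 24.
- 6/22/19: mean 60/47 = 1.277, S = 22 + 4 × 19 − 60²/47 = 21.40.

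*Pure COMT main effect, 0.5 SD per allele.*

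- Single session: λ = 0.25 × 24 = 6.0, rejection 0.553; λ = 0.25 × 21.40 = 5.35, rejection 0.503.
- Session mean: its variance is (1 + ρ)/2, so for 12/23/12, λ = 6.0/0.75 = 8.0 (0.686) or 6.0/0.90 = 6.67 (0.601). For 6/22/19 the results are 0.632 and 0.549.
- Change: the main effect cancels, λ = 0, rejection 0.05.

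*Pure interaction, 0.6 SD of the paired difference per allele.*

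- Change: λ = 0.36 × 24 = 8.64 (0.721); λ = 0.36 × 21.40 = 7.71 (0.668).
- Tolcapone-session level: the paired difference has variance 2(1 − ρ). If the whole effect falls in that session, 12/23/12 gives 0.721 (ρ = 0.5) or 0.343 (ρ = 0.8). If it is split evenly between sessions, 0.227 or 0.116. For 6/22/19 the four values are 0.668, 0.310, 0.207 and 0.108.

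So a level test does not always lose power, but it cannot separate a main effect from an interaction. A change-score test can.

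**Step 3. What the analysis could show even if fully specified.** With λ = f² × n:

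| n | Groups | Power at f = 0.25 | f for 80% power |
|---|---|---|---|
| 47 | 3 | 0.297 | 0.469 |
| 47 | 2 | 0.389 | 0.418 |
| 55 | 3 | 0.345 | 0.431 |
| 55 | 2 | 0.445 | 0.385 |

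For 12/23/12, f = 0.469 corresponds to 0.469/√(24/47) = 0.656 SD per allele, or about 1.3 SD between homozygotes. This agrees with the plan's own statement that genotype is not powered. An added genotype test on weekend drinking (n = 55) would have 34% to 44% power at f = 0.25, so a null result would say little.

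**The case for a change.** The best case for a change is that a secondary outcome should have a test that can be identified from the text, and this one does not. Calling the analysis exploratory does not say which variable went into it. The two sections also state different questions: COMT and decision-making in one, genotype and response to tolcapone in the other. Clarifying would cost a sentence and at most one or two ANOVAs on existing data.

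Much of this stands. The variable and the groups are not pinned down, and the outcome phrase is wider than the test. But it establishes an unclear sentence, not a wrong analysis, because one of the two supported readings gives exactly the right test.

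The weekend-drinking part is weaker. The Genetic Analysis section confines the genotype aim to decision-making, and nothing obliges an exploratory genotype question to cover the primary outcome. The correlation sentence has to add which effects it means, so the bare phrase in the outcome list need not include drinking.

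The rejection rates above show the logic but do not measure harm in this trial. They rest on assumed counts, correlations and a main effect of a full SD between homozygotes.

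**Conclusion.** The mismatch in wording is real, but it does not show a faulty analysis. It is a gap that an analyst can fill sensibly from the same section: take the DDT outcome as listed, the tolcapone-placebo change in ICR, and compare it across COMT genotypes. Done that way, the one-way ANOVA is the genotype-by-drug test. An ANOVA on ICR level would instead answer the aim in the Genetic Analysis section and should be read only as a COMT main effect.

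The possible damage is confined to how one exploratory result is interpreted. The primary outcome, its paired t-test and the sample size of 48, which was set on lab-bar drinking, are untouched. The analysis is already declared unpowered: 30% at f = 0.25 with 47 subjects in three groups. The contrast between readings (50% to 69% rejection against 5% for a pure main effect) depends wholly on assumed genotype counts, correlations and effect sizes. Which variable was actually analysed cannot be checked here, since the results are not part of the document.

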### *Experimental Design*

Subjects participated in a total of seven visits: Screening, Drug Dispensation x 2, Compliance x 2, and Laboratory Session x 2 (described below). Upon completion of both the first randomized double blind drug cycle and a drug washout, subjects crossed over to complete the second drug cycle.

To increase subject retention, and given previous work that even a single dose of tolcapone can influence decision making (Kayser et al., 2012), we evaluated a 5-day treatment period. This 5-day dosing regimen included a weekend, thereby both allowing us to capture self-reported weekend drinking (Friday-Sunday) on study drug, and also permitting subjects to return on the final day of the treatment window for the Laboratory Session (on either a Monday or a Tuesday evening). Based on previous work with this subject population, we felt that subjects might display higher drinking over the weekends and therefore that we would be best able to capture a drug effect during this time.

The trial was registered at ClinicalTrials.gov, NCT 02740582.

Figure 1

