Female subjects were administered a pregnancy test, and were required to be non-pregnant, non-lactating, and using a reliable contraceptive method. Exclusion criteria included a positive urine drug screen (with the exception of THC), or use of any illicit substance within 72 hours of the start of the study; current attempts to either reduce or eliminate alcohol consumption (e.g. via current enrollment in an alcohol or drug treatment program); history of alcohol related complications (e.g., liver failure/cirrhosis, pancreatitis, esophageal varices); abnormal results on tests of liver injury (alanine aminotransferase (ALT) or aspartate aminotransferase (AST) values greater than the upper limit of normal); regular use of any drugs with catecholaminergic actions such as SSRIs or amphetamines; and severely low or uncontrolled high blood pressure. Information about subjects' past substance use, psychiatric history, medical history, current medications, and family history of problem drinking was collected. The study clinician performed a physical examination, a 12-lead electrocardiogram, and a blood draw to evaluate markers of liver injury. To establish a baseline prior to laboratory bar sessions, subjects were also asked to perform components of a standard field sobriety test that assessed horizontal gaze nystagmus, walk-and-turn, and a timed one-leg stand. Together with evaluation of BAC, these direct measures of neurological function were used to ensure that subjects were free of alcohol-induced motor impairments prior to dismissal from the laboratory bar sessions. The screening visit concluded with the administration of behavioral inventories including the Alcohol Use Disorders Identification Test (AUDIT; (Saunders, Aasland, Babor, de la Fuente, & Grant, 1993)) and the Barratt Impulsiveness Scale (BIS; (Patton, Stanford, & Barratt, 1995)). Eligible subjects were scheduled into groups of 4-8 subjects for study drug administration.

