#### *Weekend Drinking*

Subjects were instructed on “standard alcoholic drink” volumes and provided an information card for reporting weekend drinking. Subjects were contacted via a HIPAA compliant text message system each day during medication administration to capture the number of alcoholic drinks the subject had consumed the previous night. To confirm standard drink values, the type, amount, and volume of alcohol were reviewed in person with the study staff at the Compliance Check. “Weekend drinking” was calculated as the total number of alcoholic drinks from Friday to Sunday.

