#### *Laboratory Session*

Subjects arrived at the clinic for the laboratory session (in groups of 4-8 subjects) on a Monday evening (for subjects started on a Thursday) or Tuesday evening (Friday start). Subjects were asked to fast for 1 hour prior to the start of the session and were drug screened and assessed for acute intoxication upon arrival. Those subjects with a positive screen or BAC were not permitted to consume alcohol. Subjects ingested the final dose of study medication immediately prior to completing the tasks below.

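### With one cycle per condition, the correlation between tolcapone effects on weekend drinking and ICR cannot separate a drug relationship from ordinary cycle-to-cycle covariation or a shared period shift

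*Combined protocol and SAP*

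**What the plan says.** The design is a two-cycle crossover (Experimental Design): "Upon completion of both the first randomized double blind drug cycle and a drug washout, subjects crossed over to complete the second drug cycle". Each subject therefore contributes one cycle on each treatment.

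Weekend drinking is one Friday-to-Sunday total per cycle (Weekend Drinking). ICR is one value per cycle, from the session that closes the same 5-day window (Laboratory Session): "Subjects arrived at the clinic for the laboratory session (in groups of 4-8 subjects) on a Monday evening" for Thursday starters, and on Tuesday for Friday starters. ICR thus follows the weekend count by a day or two.

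The Statistical Analysis section says of the two outcomes: "Change in weekend drinking and ICR on tolcapone versus placebo were assessed using a within subjects paired t-test". It then adds: "The relationship between tolcapone effects on weekend drinking and ICR was assessed with correlation analysis". It does not give the type of correlation, the number of subjects, any period or sequence term, or any limit on interpretation. The correlation is not among the listed secondary outcomes. At most 47 subjects can enter it, the delay-discounting set being the smaller one: "leaving 47 subjects for the DDT analysis".

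**The concern.** A subject's tolcapone effect on either outcome is a single difference between two weeks. It contains that subject's response to the drug, the ordinary change in that subject from one week to another, and any general shift between the first and second cycle. The paired t-test averages over subjects, and randomised order protects the average. A correlation across subjects has no such protection: it uses the spread of the differences, and all three components feed that spread.

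This is the only planned analysis that links the drug's effect on decision making to its effect on drinking. If a heavy weekend, or a passing state such as stress, also raises ICR at the following session, the two differences will correlate even if tolcapone does nothing. The wording of the plan would then label that link a relationship between drug effects.

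**Working it through.** **Inputs.** From the documents: one cycle per condition; n = 62 − 7 = 55 completing weekend drinking, 55 − 5 = 50 completing both laboratory sessions, 50 − 3 = 47 for ICR. Assumed, because the documents give no value: the within-person correlation r_w between a cycle's drinking and that cycle's ICR, and any period shift. The differences are read as tolcapone minus placebo, which follows from the preceding sentence of the plan although no formula is written out.

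**The plan's own figure.** None is given for the correlation. The sample size reproduces: for a difference of 0.5 and SD 1.2 (ratio 0.417), a two-sided paired t-test at 0.05 needs 48 subjects (power 0.807).

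**Step 1: what the labels contribute.** Let x and y be a subject's differences in drinking and ICR. Swapping the two cycles turns (x, y) into (−x, −y), so xy, x² and y² do not change. In

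r = (Σxy − n·x̄·ȳ) / √[(Σx² − n·x̄²)(Σy² − n·ȳ²)]

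only the means x̄ and ȳ depend on which cycle was tolcapone. In simulation with n = 47, reassigning all labels at random changes r by about 0.02 on average when both mean effects are zero. When both are 0.417 SD (the plan's own standardised laboratory-bar effect), the average change is 0.07 to 0.22, depending on the underlying correlation and on whether the two effects have the same direction. That movement comes from the mean effects and does not show that individual effects are related.

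**Step 2: what r estimates.** Write x = τ_W + Sπ_W + (week noise) and y = τ_I + Sπ_I + (week noise), where τ are individual drug effects, S = ±1 is treatment order and π are period shifts. With drug effects independent of noise and order balanced,

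cov(x, y) = cov(τ_W, τ_I) + π_W·π_I + 2·r_w·σ_W·σ_I.

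One pair of differences per subject yields only the sum. With no drug and no period effect, the correlation of x and y is simply r_w.

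**Step 3: no drug effect, n = 47.** Critical |r| = 0.288, or atanh(0.288)·√44 = 1.963 on the Fisher scale. At r_w = 0.3 the shift is 0.3095 × 6.633 = 2.053, so the rejection probability is Φ(2.053 − 1.963) = 0.54. Simulation gives:

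| Assumed r_w | Correlation test significant | Paired t-test significant |
|---|---|---|
| 0 | 5% | 5% |
| 0.1 | 10% | 5% |
| 0.2 | 27% | 5% |
| 0.3 | 54% | 5% |
| 0.4 | 81% | 6% |

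**Step 4: period shift alone.** With r_w = 0 and a shift of 0.5 SD in both differences, the induced correlation is 0.25 / (1 + 0.25) = 0.20. Simulation gives 26 to 27% rejection, in line with the 0.2 row. Adjusting both differences for order brings this back to 5%. The same adjustment does not touch Step 3: at r_w = 0.3 rejection stays at 53%.

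**Step 5: the opposite case.** Let individual drug effects truly correlate at 0.8, with mean zero, variance equal to that of the noise in the difference, and r_w = 0. The correlation of the differences is 0.8 / (1 + 1) = 0.40, and the test rejects in 83% of trials. With no drug effect and r_w = 0.4 it rejects in 81%. The two situations look alike. A test of r that re-randomises labels within subject rejects in only 4% of trials in this case, so the labels offer almost no help in telling them apart.

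**The case against.** The strongest reply is that the plan makes no causal or mediation claim. It says a relationship was assessed, in an analysis outside the listed outcomes, and the results are not in the documents. That stands: the point concerns how the quantity is named and what may be concluded from it, and it is modest in weight.

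A second reply is that everything beyond 5% rests on unstated quantities. That also stands. With r_w = 0 and no shared period shift, the test holds its level, and nothing in the documents supports a particular value.

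Several stronger readings are tempting and are not supported.

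- A reader might infer that the correlation is blind to drug effects. It is not: Step 5 shows that it rises when individual effects are truly related. What it cannot do is isolate them.
- A reader might take the 10 to 81% as an inflated error rate. When r_w is not zero the differences really are correlated, and the test is right to reject zero correlation. The error lies in attributing the association to the drug.
- A reader might conclude that treatment labels hardly matter to r in general. That holds for swapping one subject or for small mean effects, but not for relabelling everyone when both mean effects are sizeable.
- A reader might conclude that adjusting for order is pointless, or that it cures the problem. It removes the period part only.

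**Conclusion.** The concern holds as a limit on attribution. With one cycle per condition, the planned correlation mixes related individual drug responses, ordinary cycle-to-cycle covariation and any shared period effect, and nothing in the plan separates them. If the drug does nothing, a significant result at n = 47 occurs in about 10% of trials at a within-person correlation of 0.1 and 54% at 0.3, or in 26 to 27% from a shared 0.5 SD period shift alone. These figures assume normally distributed differences, an ordinary product-moment correlation and the stated values of r_w and period shift. The algebra in Step 1 needs none of these assumptions. The documents do not support extending the criticism to the paired comparisons of drinking and ICR, or to the sample size.

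**What to change.** In the Statistical Analysis section, change the correlation sentence in three ways:

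- Compute the correlation on differences adjusted for treatment order, for example as residuals after regressing each difference on sequence. State the type of correlation and the number of subjects.
- Describe it as an exploratory within-person association between the two cycles.
- State that it is not to be read as a relationship between tolcapone effects, or as evidence that the drug's effect on impulsivity accounts for its effect on drinking.

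The cost is one reworded sentence, one degree of freedom (critical |r| moves from 0.288 to 0.291 at n = 47) and a weaker conclusion from a supporting analysis. No new data are needed. The reworded result will still include any varying drug response, which is why the description has to stay neutral about cause.
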